6.1 Procedures and Assessments

Provide a thorough description of all study procedures, assessments and subject activities in a logical and sequential format. Indicate what study activities happen when and where, including, when applicable, a study schedule that notes number and length of study visits for subjects.

Table 3. Outline of Study Session	
TIME	PROCEDURE
8:00-8:30	Determination of session eligibility (urine and breath tests)
8:30-8:50	Nicotine gum break (smokers), generic chewing gum break (non-smokers)
8:50-9:00	Nicotine blood sample
9:00-9:05	POC glucose check
9:05-9:15	Nares exam
9:15-10:00	Relaxation phase (both smokers and non-smokers)
10:00-10:06	Spray administration
10:10-10:30	Equipment setup
10:30-11:40	Go-No/Go task
11:40-11:45	Olfactory function test
11:45-12:00	Discharge procedure (POC measurement)

Study session will begin at 8:00 AM. First, the research coordinator will ensure that the lab has a signed consent form on file from the participant. Smokers will be instructed to smoke the normal amount of cigarettes they usually smoke upon waking prior to each session, then refrain from smoking until the end of the session. For example, if they usually smoke 2 cigarettes upon waking, they will be instructed to smoke 2 cigarettes prior to the first session (30 minutes upon waking) and 2 cigarettes prior to the second session (30 minutes upon waking). Participants will be asked if they have had breakfast. If they did not eat breakfast that morning, research coordinator will give them a granola bar and re-emphasize the importance of eating breakfast. Next, from 8:00 AM to 8:30 AM, urine and breath samples will be obtained by the study coordinator, for verification of absence of alcohol intake. A urine sample will be obtained to rule out illicit drug intake and pregnancy. See Section 6.2 Specimen Considerations for more information on urine sample collection and analysis protocol.

At 8:30, smokers will take a 20-minute nicotine chewing gum (Nicorette gum, 4mg) break, and non-smokers will take a 20-minute generic, non-nicotine chewing gum break. As per the instructions given by Nicorette, smokers will be instructed chew the gum slowly until they experience a tingling sensation, then to place the gum between their cheek and gum until the tingle subsides and repeat until most of the tingle is undetectable. Non-smokers will be instructed to chew the generic gum at their own pace.

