At 8:50 AM, research coordinator will administer VANES Questionnaire on REDCap. Following completion of the VANES Questionnaire, a nicotine blood sample will be taken by the study nurse to ensure comparable nicotine levels in participants between the two sessions. In order to synchronize the procedure in both smokers and non-smokers, a blood sample will be taken from non-smokers as well.

Point of care measurement will occur at 9:00, followed by a physical exam of the nares at 9:05. POC glucose will be checked to ensure normal glucose levels. Study nurse will be responsible for conducting nares physical examination. Subjects will relax from 9:15 to 10:00. The blood draw at 8:50 (for the purpose of nicotine level analysis) can cause a rise in cortisol, which remains high for approximately 60 min. The purpose of the relaxation phase is to wait for the stress response to normalize, thereby minimizing its impact at the time of treatment administration and event related potential testing.

Spray administration will occur at 10:00 AM as one spray in each nostril every 3 minutes for the total of 6 sprays (two sprays at 10:00, two sprays at 10:03, two sprays at 10:06). The same spray protocol will be followed for administration of both intranasal insulin and placebo. AeroPump delivers 0.1 ml of liquid per spray. Since the concentration of insulin in Novolin R is 100 IU/mL, six sprays will deliver the 60 IU intranasal insulin dose. See Section 6.3 Drug Product Considerations for more information on insulin and placebo intranasal administration preparation.

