11.0 Data and Safety Monitoring

Addresses how problems/side effects will be identified and handled:

Subjects will be asked to report any adverse events by specific questioning. The questions will specifically refer to symptoms of hypoglycemia and local irritation, but they will include additional questions about general adverse events as specified in the Consent Form. In addition, subjects will be asked to report any adverse events not listed on the Consent Form. The clinical course of each event will be followed until resolution, stabilization, or until it has been determined that the study treatment or participation is not the cause. If any serious events are detected, they will be followed up to determine the final outcome. Following completion of the study, participants will be instructed to report any adverse events and if the Principal Investigator determines that it is possibly related to the study treatment or participation, will be recorded and reported.

Subjects will be asked to report any adverse events they may have experienced related to the spray that was administered, the Nicorette nicotine gum, and the general study protocol. Information on all adverse events will be recorded immediately on the "Adverse Event Questionnaire" form provided by the PI's lab. The "Adverse Event Questionnaire" lists all the expected AEs of intranasal insulin and nicotine gum as listed in the Nicorette information sheet and IND#120700 for intranasally administered Novolin R. In addition, blank space is included for study participants to list any additional AEs not listed on the form.

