Anticipated and non-serious adverse events will be collected and entered into the study database for the purpose of comparing their incidence following intranasal insulin in comparison to the placebo spray administration.

For studies that are minimal risk, describe how potential problems will be monitored and handled (e.g., breaches of confidentiality, emotional upset): This is not a minimal risk study.

For research involving more than minimal risk to subjects, describe: Who will monitor adverse events (AEs) and unanticipated problems (UPs) involving risks to subjects or others and when events will be assessed: All research staff will be responsible for collecting AEs and UPs, but the ultimate responsibility and classification determination will rest with the PI. Whereas the study

coordinator/postdoc will sign the completed Adverse Event form, that form will be given to the PI who will use the “Adverse Event Tracking Form” for final classification of the AE. It will be documented on the form whether the event listed in the blank space on the Adverse Event form falls into anticipated/unanticipated and whether the nature of the event is serious/non-serious. In the event of unanticipated and/or serious event, the resolution of the AE will be tracked by the PI and all communications will be related to the Institutional Review Board.

How AEs or UPs will be recorded and communicated amongst research team members and who is responsible for making the reports: At the end of each testing session, participants will be asked to complete “Adverse Event Questionnaire”. The research member facilitating the session and the PI will review and sign the form. The PI will record the determination of expectancy and seriousness of each event in the “Adverse Event Tracking Form”, and will communicate the result of this determination using UIC HSPP form “Prompt Reporting to the IRB”.

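### The Adverse Event Questionnaire has no pre-spray baseline, so systemic symptoms that nicotine gum shares with insulin can enter smokers' counts of events following each spray and dilute the comparison (minor)

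*Combined protocol and SAP*

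**What the plan says.** Section 6.1 sets the order of the session. "At 8:30, smokers will take a 20-minute nicotine chewing gum (Nicorette gum, 4mg) break", while "non-smokers will take a 20-minute generic, non-nicotine chewing gum break". A nicotine effects scale (VANES), a blood draw, a finger-stick glucose check and a nares examination follow. Then "Subjects will relax from 9:15 to 10:00", with no assessment scheduled in that slot. "Spray administration will occur at 10:00 AM as one spray in each nostril every 3 minutes". Section 6.0 makes the two sessions identical apart from the spray, so the gum is given in both.

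Section 11.0 describes the safety record. Participants are asked about events "related to the spray that was administered, the Nicorette nicotine gum, and the general study protocol". One form, the Adverse Event Questionnaire, carries the expected events of both intranasal insulin and nicotine gum, with space for others. On timing the section says: "At the end of each testing session, participants will be asked to complete" this form. It also says that events are recorded on the form immediately. The principal investigator then classifies each event by expectancy and seriousness. Anticipated, non-serious events go into the database for "comparing their incidence following intranasal insulin in comparison to the placebo spray administration".

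Two other records exist. Section 7.0 has pain, burning, taste, cough and other local irritation rated from 1 to 10 after each of the three spray rounds. Section 6.1 places VANES at 8:50, after the gum and before the spray.

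**The concern.** The planned comparison concerns events that follow a spray, but the plan describes no data item showing that an event did follow it. By 10:00 smokers have had a nicotine dose, and all participants have had a needle stick, a finger-stick and a nasal examination. If the form is completed at the end of the session, a participant with sweating or a headache since 9:00 ticks the same box as one whose symptom began at 10:15.

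The expected-event lists in Section 6.3 overlap. Sweating and tingling around the mouth are listed for insulin; diaphoresis and paresthesia are listed for the gum. Dizziness and headache are expected gum events, and both were reported under insulin in the earlier trial (Section 2.0, Table 2). Asking a participant which product caused a symptom common to both is weak evidence, and no rule says how the answer would be used.

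At stake is the ability to see an insulin signal in these terms, and the meaning of the absolute rates. The monitoring board reviews the number and nature of events, and the stopping rules refer to side effects that are more frequent than expected (Section 11.0). Rates that include a gum background are harder to read for that purpose.

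**Working it through.** **Timing (Section 6.1, session table).** Gum start to spray: 8:30 to 10:00 = 90 minutes. Gum end to spray: 8:50 to 10:00 = 70 minutes. Gum end to the discharge slot: 8:50 to 11:45 = 175 minutes. Last spray to the discharge slot: 10:06 to 11:45 = 99 minutes. A form completed only at the end thus looks back over a period that includes the gum and 70 minutes between gum and spray.

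**Inputs.** The plan gives no adverse event rate, test or power, so there is no figure to reproduce. From Section 12.0: 60 smokers. Assumed for illustration: spray-caused events in pI = 15% of insulin sessions and pP = 5% of placebo sessions; gum-caused events in a proportion g of sessions, g = 0, 10, 20 or 30%, the same in both sessions; exact two-sided McNemar test at 0.05.

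**Observed rates.** With gum and spray events independent within a session, the observed rate is 1 − (1 − g)(1 − p). At g = 10%: insulin 1 − 0.90 × 0.85 = 23.5%; placebo 1 − 0.90 × 0.95 = 14.5%. The difference is (1 − g)(pI − pP) = 0.90 × 0.10 = 9.0 points. If pI = pP, the difference is zero for every g, so the gum creates no false difference.

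**Discordant pairs.** The power loss depends on whether the same smokers react to the gum both times. The two extremes are:

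- Gum events independent between sessions, with oI and oP the observed rates: insulin-only b = oI(1 − oP), placebo-only c = oP(1 − oI). At g = 10%: b = 0.235 × 0.855 = 0.201; c = 0.145 × 0.765 = 0.111.
- Gum events fully concordant: b = (1 − g)pI(1 − pP), c = (1 − g)pP(1 − pI). At g = 10%: b = 0.90 × 0.15 × 0.95 = 0.128; c = 0.90 × 0.05 × 0.85 = 0.038.

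Power sums over the number of discordant pairs, binomial(60, b + c), the chance that the exact binomial test of an even split gives p ≤ 0.05 when insulin-only pairs have share b/(b + c).

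| Gum-event rate g | Observed insulin v placebo | Difference | Power, independent | Power, fully concordant |
|---|---|---|---|---|
| 0% | 15.0% v 5.0% | 10.0 points | 33% | 33% |
| 10% | 23.5% v 14.5% | 9.0 points | 17% | 29% |
| 20% | 32.0% v 24.0% | 8.0 points | 11% | 24% |
| 30% | 40.5% v 33.5% | 7.0 points | 8.5% | 20% |

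The apparent insulin rate rises from 15% to between 23.5% and 40.5%, whichever pattern holds between sessions.

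**The case against.** Several stronger readings are tempting, and the documents do not support them.

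*Safety is scored only once, with no symptom record before the spray.* Local effects are rated after each spray round, and events are also to be recorded immediately. Nasal irritation, the commonest insulin event in Table 2 (7 occurrences; no other term exceeds 2), is therefore tied to the spray. VANES is completed before the spray, although its items are not shown and nothing links it to the adverse event comparison. What remains uncovered is systemic symptoms.

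*Gum symptoms are counted as spray events.* The documents show that they can be, not that they will be. Participants are asked about spray and gum by name, and the Adverse Event Questionnaire and Tracking Form are attachments not included here; either may hold an onset or source field. The overlap is also partial: anosmia, visual disturbances, shaking and hunger are not on the gum list, so a term-by-term comparison of those would be little affected.

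*The comparison is biased for or against insulin.* It is not. The gum is the same in both sessions, and the crossover removes any directional effect under the null.

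*The smoker v non-smoker safety contrast is confounded.* It would be if it were made, but Section 11.0 plans only insulin against placebo. Non-smokers also carry no nicotine background, so the loss shown above concerns half the sample.

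Finally, the comparison has only about one-third power on these assumptions even with no gum events, and it does not touch the go/no-go endpoint. That stands, and it limits the severity. It does not remove the point: a planned comparison of events following each spray still needs a way to identify them.

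**Conclusion.** The point holds for systemic terms that gum and insulin share. The plan describes no pre-spray adverse event baseline, onset time or attribution rule, so symptoms already present in smokers at 10:00 can enter the incidence comparison. The effect is dilution of the within-person contrast and inflation of absolute rates in smokers.

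The size rests wholly on assumed rates. With 15% v 5% spray-caused events in 60 smokers, power falls from 33% to 17–29% at a 10% gum-event rate and to 8.5–20% at 30%. The lower end of each range assumes that gum events are independent between a person's two sessions, the upper end that they are fully concordant. Since the same people repeat the same gum, some concordance is plausible, so the lower end should not be quoted alone. The calculation also pools all terms into a single any-event outcome, which overstates the loss for terms that do not overlap.

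Severity: minor. This is a descriptive safety comparison with no false-positive bias and with separate local ratings already in place.

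**What to change.** Have participants also complete the same Adverse Event Questionnaire at 9:15, at the start of the relaxation phase. State in Section 11.0 that the insulin v placebo comparison counts only events that are new, or worse than at 9:15, after the 10:00 spray. Continue to report all events for general safety.

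At 9:15 the form comes 25 minutes after the gum ends and after the blood draw, finger-stick and nares examination, and it leaves most of the 45-minute rest undisturbed. A symptom that starts between 9:15 and 10:00 would still look new; recording on the end-of-session form whether each symptom began before or after the spray would deal with that.

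The cost is one more self-completed form, about five minutes per session, with no added staff and no change to any treatment or schedule of dosing. Asking twice may prompt slightly more symptom reports, equally in both sessions.

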3.0 Objectives/Aims

Identify hypotheses being tested/primary endpoints/primary purpose of the protocol: The aim of the proposed work is to evaluate go/no-go accuracy as a neurologic biomarker of smoking behavior. Our hypothesis is that following intranasal insulin administration, smokers will have an improved go/no-go accuracy.

Study duration: This duration of the research study is 2 years starting January 2018 – January 2020.

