6.0 Study Design and Procedures

List any collaborating sites where human subjects research will be performed, and describe the role of those sites and collaborating investigators in performing the proposed research (if applicable): This study will be only conducted at University of Illinois. Study space will be rented at Center for Clinical and Translational Science. In addition, UIC nurse will be responsible for performing nasal examination and collecting blood samples. Study personnel – working out of the PI's laboratory - will ensure regulatory compliance, recruit participants, as well as collect and analyze the data. The PI's lab is located on the first floor of UIC College of Pharmacy. Study materials, equipment and all paper copies will be locked in the office of research staff affiliated with the study.

Describe the study design. The description should be capable of meeting the study objectives: This is a two group, two session study. The only eligibility criteria separating the two groups is the smoking status, otherwise the study population will consist of healthy volunteers. Following successful completion of the "Initial Survey", study participants will be scheduled for a 3-hr In-Person Screening visit. At the in-person screening, participants will 1. be consented, 2. provide urine and breath samples, 3. complete surveys, and 4. receive study instructions. After the completion of the "In-Person Screening", study participants will be scheduled for two study sessions, separated by a minimum of 1 week. During the study session, in random order, study participants will receive either intranasal insulin (60 IU) or placebo. This is a cross-over study –participants receiving intranasal insulin will receive placebo next, and vice-versa. Please refer to Table 1 for a summary of the study

session. The sessions will be identical, other than participants receiving intranasal insulin or placebo in random order.

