The composition of the Data and Safety Monitoring Board (DSMB) and how frequently the DSMB meets, if one has been formed for the study: The Data and Safety Monitoring Board will be chaired by a physician – [name] – and two additional members – [name] and [name] – who are also clinicians. [name] is the Deputy Director of the Clinical and Translational Science Center at the University of New Mexico and a Regents’ and Distinguished Professor of Medicine. [name] is an Associate Professor at the University of New Mexico’s College of Pharmacy. [name] practices as a pharmacist clinician in the University of New Mexico Family Medicine clinics. The DSMB will meet every six months on a teleconference call. The type of safety information that will be assessed is the number and nature of adverse events that have been reported in the time since the previous call, results of olfactory function testing (i.e. Sniffin’ Sticks), POC glucose testing as well as the outcome of events discussed in previous meetings. The summary of the meetings and recommendations will be reported to the Principal Investigator as well as Human Research Protections Office within 15 days after the meeting. The board will meet on an interim basis (within 7 days) in a case of expedited cases in which the probability of treatment causality is high or a case of a change to the risks or potential benefits of the research (such as safety monitoring indicates that a particular side effect is more severe, or more frequent than initially expected). In such cases, the Principal Investigator will supply results of interim analysis including plans/safeguards to keep any data or DSMB analyses confidential.

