Describe stopping rules for the study: Stopping rules for the study will apply to expedited cases in which the probability of study treatment causality is high or a case of a change to the risks or potential benefits of the research (such as safety monitoring indicates that a particular side effect is more severe, or more frequent than initially expected). In the case of an expedited event, the study will be stopped until further information is gathered and a potential plan is formulated through consultation with the IRB.

Describe what occurs if a subject withdraws prematurely: The PI and an appointed research team member will provide guidance to participants on the most appropriate method of discontinuation based on where they are in the study protocol. Recommendations will be given based on what procedures the subject has completed. For example, if the participant decides to withdraw participation immediately after receiving a spray, researchers will counsel the participant on common side effects they may experience. Researchers will provide a discharge summary of the session based on what the participant has completed. The team will provide supportive care to subjects as needed following all premature discontinuations.

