12.0 Statistical Considerations

If a study incorporates qualitative rather than quantitative methods, indicate this and describe qualitative analysis and disregard the rest of this section: This study does not incorporate qualitative data analysis.

Describe how the data will be examined and statistically analyzed to answer the objectives: Go/no-go accuracy will be evaluated in a 2 x 2 repeated measure ANOVA, with group, treatment and treatment x group interaction entered into the model.

Provide a brief sample size calculation or description of sample size calculation. Include methods and assumptions such as loss to follow-up, as appropriate: Effect size is estimated from Luijten et al (2011). In that study, effect size was 0.24.

We anticipate 120 participants completing the study. An a priori power analysis was conducted using G*power 3.1.9.2 for an ANOVA test, repeated measures and within-between interaction. With 2

within and 2 between factors; a base correlation=0.6; power=0.95; alpha=0.05, the total of 120 participants (60 per group) is required to capture an interaction between group and treatment on ERN.

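### The DSMB's routine adverse-event report covers only the interval since the last call, with no cumulative counts by treatment, so it is less sensitive than it could be to an excess on insulin

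*Combined protocol and SAP*

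**What the plan says.** Section 11.0 (Data and Safety Monitoring), in the item on the DSMB, sets the schedule: "The DSMB will meet every six months on a teleconference call". For adverse events the board assesses "the number and nature of adverse events that have been reported in the time since the previous call". It also receives smell-test results, point-of-care glucose results and follow-up on events it has already discussed. The since-last-call limit is attached to adverse events only; smell and glucose carry no stated window. No cumulative total, number of sessions dosed or split by treatment is specified.

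The same item calls for an extra meeting within 7 days if, among other things, "safety monitoring indicates that a particular side effect is more severe, or more frequent than initially expected". The stopping-rules item of Section 11.0 repeats that condition. Neither gives a threshold, a time window or a comparator. At an extra meeting the principal investigator supplies an interim analysis.

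Section 11.0 also says that anticipated, non-serious events are entered in the database so that their incidence on insulin and placebo can be compared. It gives no timing for this comparison and does not assign it to the board.

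**The concern.** The trigger is a frequency, and a frequency needs a numerator, a denominator and something to compare it with. The routine report as written supplies a numerator for about six months. Earlier events come back only as individual outcomes, not as counts.

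The treatment split matters here because Section 7.0 says the placebo itself commonly causes nasal burning and irritation. A count pooled over both sprays cannot separate an effect of insulin from an effect of concentrated saline. The design offers a within-person comparison ("participants receiving intranasal insulin will receive placebo next, and vice-versa"), but the board's report is not set up to show it.

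At stake is how soon, and how reliably, the board would notice a moderate excess on insulin that is spread evenly over the study. Section 11.0 itself says that the study is not minimal risk.

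**Working it through.** The plan gives no figure for how much data each call covers, so there is none to reproduce. The calculation below supplies one.

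**Inputs.** Completers: 120 (Section 12.0, "We anticipate 120 participants completing the study"). Duration: 24 months (Section 3.0, "This duration of the research study is 2 years"). Calls: every 6 months (Section 11.0). Each participant has one insulin and one placebo session (Section 6.0). The event rates are illustrative assumptions.

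**Participants per interval.** 24/6 = 4 intervals; 120/4 = 30 with even accrual. If testing takes 18 or 12 months: 120/3 = 40 or 120/2 = 60.

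**Yardstick.** The plan names no test, so I use an exact two-sided McNemar test at 5%, with independent responses within a person. With rates pI (insulin) and pP (placebo), the discordant probabilities are pI(1 − pP) and pP(1 − pI). For 15% v 5% these are 0.15 × 0.95 = 0.1425 and 0.05 × 0.85 = 0.0425, so 30 people give on average 30 × 0.185 = 5.6 discordant pairs. Five pairs all in one direction give p = 2 × 0.5^5 = 0.0625; six give 0.031. A slice of 30 therefore often has too few pairs to reach 5% at all. For 10% v 2% the mean is 30 × 0.116 = 3.5 pairs.

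**Detection.** At least one of four slices = 1 − (1 − p)^4, where p is the single-slice value.

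| Insulin v placebo | One slice (30) | At least one of 4 | Cumulative 60 / 90 / 120 |
|---|---|---|---|
| 15% v 5% | 0.0986 | 34% | 33% / 53% / 68% |
| 25% v 10% | 0.2079 | 61% | 50% / 69% / 83% |
| 10% v 2% | 0.0441 | 17% | 29% / 52% / 69% |
| 20% v 10% | 0.0963 | 33% | 25% / 38% / 51% |
| 30% v 10% | 0.3579 | 83% | 73% / 90% / 97% |

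The first three rows are the moderate excesses summarised in the verdict. The fourth shows that cumulative review does not rescue every case. The fifth is a large excess.

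**At the third call.** On even accrual the fourth call comes as testing ends, so the third is the more useful comparison. At least one of the first three slices, 1 − (1 − p)^3, gives 27%, 50% and 13% for the first three rows, against 53%, 69% and 52% with cumulative data at 90.

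**Signal in the cumulative data but in no slice.** By simulation, when the data at 120 reach 5%, no single slice had done so in 54% (15% v 5%), 31% (25% v 10%), 77% (10% v 2%), 47% (20% v 10%) and 15% (30% v 10%) of trials.

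**The trigger on its own terms.** The trigger compares observed with expected, not insulin with placebo. Take the lower rate as the expected rate and apply a one-sided 5% exact binomial test to 30 insulin sessions. The critical counts are 5, 7 and 3 events for expected rates of 5%, 10% and 2%. Detection in one slice is 48%, 65% and 59%. In at least one of four it is 1 − (1 − 0.4755)^4 = 92%, 1 − (1 − 0.6519)^4 = 98.5% and 1 − (1 − 0.5886)^4 = 97%. Cumulatively at 120 it is 98% to 99%. This too needs event counts and sessions dosed by treatment.

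**The case against.** The best case for the plan has four parts.

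- **The trigger is not a McNemar test.** Judged against an expected rate, interval data perform well: 92% or more across four calls. This stands, and it limits the claim. It does presume insulin-only counts and a stated expected rate, and the report as written promises neither.
- **The six-monthly listing is not the only route.** Section 11.0 has events monitored after each session, every form reviewed by the principal investigator, and an extra meeting available within 7 days. This also stands, although no one is assigned to track frequency and no threshold is set. The interim analysis is supplied only once an extra meeting has been called, so it cannot be what prompts the meeting.
- **The same three members attend each call and could add up what they have seen.** They could, and nothing forbids it. The text does not carry earlier counts forward, but it would be wrong to say that it discards them. Adding pooled counts still gives no treatment contrast.
- **Silence on a treatment split is not exclusion.** That is fair: the item lists types of information, not table layouts. But the adverse-event window is stated explicitly, so that part is more than missing detail.

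A reader might infer that an excess on insulin is likely to be missed, or that the trigger has little chance of firing. The documents and the figures do not support either as a general statement. The first is true of a single review of a moderate excess, and across all four reviews for an uncommon event. It is not true of a large excess, and comparing one slice with all 120 participants overlooks that the board meets four times. A reader might also take the interval limit to cover smell and glucose results; the text does not attach it to them.

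**Conclusion.** The point holds as a loss of sensitivity, not as a failure of monitoring. On the McNemar yardstick, the three moderate excesses are detected in one interval 4% to 21% of the time and in at least one of four 17% to 61%, against 68% to 83% with cumulative data at 120. The gap is widest for the uncommon event (10% v 2%: 17% against 69%).

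These figures rest on even accrual over the full 24 months, one event per person per session, independent responses within a person, and a 5% threshold that the plan does not set. Compressed testing narrows the gap: for 15% v 5%, at least one slice reaches 5% in 45% of trials with three slices of 40, and in 55% with two of 60. Positive correlation within a person tends to widen it: in one such model, 20% v 10% gives 9% in a slice and 80% at 120.

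The change is worth making because the board's own trigger is a frequency and the data needed are already to be entered in the study database.

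**What to change.** Amend the DSMB item in Section 11.0 so that each report contains two things:

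- the interval listing, as now;
- a cumulative table since the first dose, giving for each event the number of participants affected over the number of sessions dosed, by treatment.

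Show the treatments under codes that the board may open. The codes should not be the A and B of Section 1.0, which already identify insulin and placebo. For smell scores and glucose, which have no stated window, confirm that the same cumulative display by treatment is used.

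The cost is one sentence and one extra table per call, from data already collected. The downside is a few more false alarms: with equal 10% rates and the same 5% yardstick, simulation gives about a 6% chance of any signal across four cumulative looks, against about 4% across four separate slices. No change to sample size, visits or data collection is needed.
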